In orthodontic treatment, achieving proper alignment of anterior teeth is a key objective.⁶ Different ligation methods, such as elastomeric and steel ligatures, have been employed to achieve alignment.⁷ Elastomeric ligatures are preferred by orthodontists due to their ease of use and reduced chairside time, but the effectiveness is reduced overtime due to absorption and friction.⁸ Steel ligatures on the other hand require manual twisting of wire thereby increasing chairside time but provide effective engagement of wire into bracket slot and provide low friction mechanics.⁹ The duration of treatment is an important factor for both patients and orthodontists, as it can impact overall treatment efficiency and patient satisfaction.¹⁰ In a study by Reddy et al on comparison of different ligation method on time to reach alignment reported that the mean treatment time for alignment in elastomeric ligature was 176.3 ± 11.08 days while in steel ligature was 175.56 ± 9.41 days.¹¹ Another study reported the mean treatment time for alignment in elastomeric ligature was 224.95 ± 8.702 days while in steel ligature was 176.15 ± 9.81 days.¹²

This study aims to compare the mean treatment time required to achieve alignment of anterior teeth using elastomeric ligatures versus steel ligatures. By evaluating and analyzing these two

commonly used ligation techniques, we can gain valuable insights into their respective effectiveness in facilitating the alignment of anterior teeth. Owing to the contradictory results of the aforementioned studies this study would put to rest the contradictions. Ultimately, the findings from this study may contribute to informed decision-making regarding ligation methods, optimizing treatment outcomes, and enhancing patient experiences in orthodontic practice. There is lack of research on this topic in Pakistan, so this study will provide local statistics. The results can be variable across different populations due to genetic, ethnic and environmental factors.

OBJECTIVE

To determine the mean treatment time required by elastomeric ligatures and steel ligatures, in days, to achieve complete alignment of the lower anterior teeth.

OPERATIONAL DEFINITIONS

1. Littles irregularity index:

Measure of the distance in mm, using a Castroviejo caliper, of the sum of horizontal displacements of the anatomical contact points of the mandibular anterior teeth. It will be recorded as 0 (Perfect alignment), 1-3 (Minimal irregularity), 4-6 (Moderate irregularity), 7-9 (Severe irregularity), 10 (Very severe irregularity)

2. Alignment:

Littles irregularity index score of zero. Calculated by summing the distances (in mm) of the horizontal displacements of the anatomical contact points of the mandibular anterior teeth.

3. Elastomeric ligature:

O- shaped synthetic elastic of 0.1" diameter that holds the archwire in bracket slots.

4. Steel ligature:

Soft grade stainless steel wire of 0.009" thickness that holds the archwire in bracket slots.

OUTCOME

To determine the mean treatment time required by elastomeric ligatures and steel ligatures

RESEARCHER'S HYPOTHESIS

The treatment time taken to complete alignment of lower anterior teeth is shorter in steel ligature ligation than elastomeric ligature.

MATERIALS AND METHODS

Study Design: Randomized Clinical Trial

Setting: Department of Orthodontics and Dentofacial Orthopedics, Khyber College of Dentistry Peshawar.

Duration: 6 months after approval of synopsis.

Sample Size: By using Openepi,¹³ assuming the mean duration of 224.95 ± 8.7 days for Elastomeric ligature group and mean duration of 219.95 ± 9.82 days for steel ligature group¹², a sample of 90 participants per group will detect a 5 days difference in mean duration, with 95% power at 5% significance level.

Sampling Technique: Consecutive, Non-probability.

Inclusion criteria

1. Patients coming for fixed orthodontic treatment requiring premolar extraction in mandibular arch.
2. Age 12-18 years.
3. No adjunct therapeutic intervention involving functional or orthopaedic appliances.
4. Little's Irregularity index score of 7-9mm.

Exclusion criteria

1. Patients with systemic conditions and taking medications affecting tooth movement.
2. Lower anterior teeth that are missing, impacted or unerupted, or have fractured crown, restorations, Enamel Defects, Caries.
3. Poor periodontal health

DATA COLLECTION PROCEDURE

Approval of the hospital ethical committee will be taken. Patients from Orthodontics department, Khyber College of Dentistry fulfilling the inclusion criteria will be invited to take part in the study. The purpose, procedures, risk and benefits of the study will be explained to them. An informed written consent will be taken.

The subjects fulfilling inclusion criteria will be assigned to one of two groups using lottery method. Group A will receive steel ligature, while Group B will receive elastomeric ligature for wire engagement in brackets. All participants will be bonded with a metal 0.022" slot of MBT pre-adjusted appliances. Archwire sequence will be 0.012 NiTi, 0.014 NiTi, 0.018 NiTi and 0.019x0.025 NiTi until alignment is reached. Adjustment appointments will be conducted at six-week intervals. Mandibular dental casts will be taken on the day of appliance placement (T1) and then on the day when alignment is reached (T2). Littles irregularity index will be calculated on mandibular casts using Castroviejo caliper. The alignment time from the day of appliance placement to the day when alignment is reached (T2-T1) for each participant will be recorded in days. All the above-mentioned information will be recorded in predesigned proforma (see Annex I).

Bias and confounders will be controlled in the study by strictly following inclusion/exclusion criteria, and randomization. Effect modifiers include gender, age and pre-treatment irregularity, which will be controlled by randomization.

Statistical Analysis:

Data will be analyzed using SPSS (statistical package for social sciences) version 25.0. Mean and standard deviation will be calculated for numerical explanatory variables like age and time to reach alignment. Frequency and percentage will be calculated for qualitative explanatory variables like gender. Independent Samples t Test will be applied to compare time of alignment in days between two groups (steel and elastomeric) at T2. Normality of data will be checked through Shapiro-Wilk Test. In case of skewed data Mann-Whitney U test will be applied instead of independent samples t test. Confounders like age and gender will be controlled through stratification. Post- stratification Independent Samples t Test/ Mann-Whitney U test will be applied. P value less than or equal to 0.05 will be considered significant.

REFERENCES

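### The single 6-month duration is shorter than the 220-225 day alignment times behind the sample size, and enrolment and follow-up are not separated

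*Combined protocol and SAP*

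**What the plan says.** Under Materials and Methods the plan gives one time frame: "Duration: 6 months after approval of synopsis". It does not say whether this covers enrolment, follow-up or both.

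The Sample Size paragraph that follows takes its elastomeric input as "assuming the mean duration of 224.95 ± 8.7 days for Elastomeric ligature group" and its steel input as "mean duration of 219.95 ± 9.82 days for steel ligature group".

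The Data Collection Procedure ties follow-up to the event. Archwires progress through "0.018 NiTi and 0.019x0.025 NiTi until alignment is reached", and the time from appliance placement "to the day when alignment is reached (T2-T1) for each participant will be recorded in days".

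The introduction reports two earlier studies. In the first, the mean time for "elastomeric ligature was 176.3 ± 11.08 days while in steel ligature was 175.56 ± 9.41 days". In the second, which the sample size also cites, the mean time for "elastomeric ligature was 224.95 ± 8.702 days while in steel ligature was 176.15 ± 9.81 days".

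The documents give no accrual rate, no enrolment window, no end date for follow-up and no rule for a participant without a T2 date. The proforma in Annexure I has a field for the T2 date but none for withdrawal or for alignment not reached.

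**The concern.** Six months falls 36-39 days short of the steel planning mean (219.95 minus 184 or 181) and 41-44 days short of the elastomeric one (224.95 minus 184 or 181). If the line were applied as the total length, the study would close before the typical participant reached the only outcome.

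The analysis could not repair this. The planned t test, or Mann-Whitney test, uses completed times and makes no provision for censoring. Those with a T2 date at closure would be the fastest aligners, and if the arms truly differ, the missing outcomes would fall unequally between them. That would defeat the comparison the trial exists to make.

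**Working it through.** **Inputs.** Planning means and SDs: 224.95 (8.7) and 219.95 (9.82), 90 per group, from the Sample Size paragraph. Reported means and SDs from the introduction: first study 176.3 (11.08) elastomeric and 175.56 (9.41) steel; second study 224.95 (8.702) elastomeric and 176.15 (9.81) steel. Six months is taken as 182 days. Times are assumed roughly normal.

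**Step 1: reproduce the plan's sample size.** For a two-sided 5% test with 95% power, n per group = (SD1² + SD2²)(1.960 + 1.645)² / difference² = (75.69 + 96.43) × 12.99 / 25 = 89.5, rounded up to 90. This matches, so the 220-225 day means are the inputs actually used.

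**Step 2: share aligned by day 182, everyone bonded on day 1.** This is the most favourable case. P = Φ((182 − mean)/SD).

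| Source | Arm | z | P(aligned by day 182) | Expected of 90 |
|---|---|---|---|---|
| Plan's inputs | Elastomeric | (182 − 224.95)/8.7 = −4.94 | 4.0e-7 | 0.00004 |
| Plan's inputs | Steel | (182 − 219.95)/9.82 = −3.86 | 5.6e-5 | 0.005 |
| Second study | Elastomeric | (182 − 224.95)/8.702 = −4.94 | 4.0e-7 | 0.00004 |
| Second study | Steel | (182 − 176.15)/9.81 = 0.60 | 0.725 | 65 |
| First study | Elastomeric | (182 − 176.3)/11.08 = 0.51 | 0.697 | 63 |
| First study | Steel | (182 − 175.56)/9.41 = 0.68 | 0.753 | 68 |

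On the plan's inputs the total is 0.005 of 180. Counting 6 months as 184 days raises it only to 0.011.

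**Step 3: staggered bonding at means near 176 days.** Sampling is consecutive, so bonding on a single day is unrealistic. For someone bonded 30 days in, the window is 152 days. On the first study's figures Φ((152 − 176.3)/11.08) = 1.4% and Φ((152 − 175.56)/9.41) = 0.6%.

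If bonding is spread evenly over the 182 days (an assumption), the share with T2 is [(182 − mean)Φ(z) + SD·φ(z)]/182, where φ is the normal density.
- First study, elastomeric: (5.70 × 0.697 + 11.08 × 0.349)/182 = 4.3%
- First study, steel: (6.44 × 0.753 + 9.41 × 0.316)/182 = 4.3%
- Second study, steel: (5.85 × 0.725 + 9.81 × 0.334)/182 = 4.1%

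So about 4% in each case.

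**Step 4: follow-up needed on the plan's inputs.** The 99th percentiles are 224.95 + 2.326 × 8.7 = 245.2 days and 219.95 + 2.326 × 9.82 = 242.8 days. At day 245, 90 × (0.0106 + 0.0054) = 1.4 of 180 would still be unaligned. With 6 months of enrolment (an assumption), 182 + 245 = 427 days, or about 14 months.

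**The case against.** The strongest reply is that the 6 months was meant as the enrolment window. The Data Collection Procedure continues archwires until alignment and records a time for each participant, which fits open-ended follow-up better than a fixed closing date. On that reading there is no conflict, and this stands. A reader might infer that the trial is bound to stop at 6 months and collect no outcomes. The documents do not support that, because nowhere do they say that follow-up ends then. Nor do they say that it continues, and a literal reader of the Duration line could close the study at that point.

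A second reply is that the near-zero figure depends on the planning value of 219.95 for steel, which is 224.95 minus the 5-day target, while the introduction reports times near 176 days in three of four arms. This is fair, and the result does change: 70-75% of participants in those arms would have T2. But that needs everyone bonded on day 1. Spread over the window, the share drops to about 4%.

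A reader might also infer from "Adjustment appointments will be conducted at six-week intervals" that T2 is known only to the nearest visit, so that the stated power is overstated. The plan defines T2 as the day alignment is reached, with a cast taken that day. Any loss of power would depend heavily on where visits fall relative to the means. That is a separate question and forms no part of this point.

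**Conclusion.** The point holds conditionally. If 6 months is the total study length, it cannot deliver the primary outcome: essentially none of 180 participants on the plan's own inputs, about 72% of steel against almost no elastomeric on the second study's means, and 70-75% in both arms on the first study's means only with everyone bonded on day 1. If it is enrolment only, the conflict disappears, but the plan leaves the true calendar, about 14 months on a 6-month enrolment, unstated. Either way the line needs correcting or redefining before the trial starts.

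The figures rest on roughly normal times and 182 days for 6 months. The 4% figure also rests on even bonding, and the 14 months on 6 months of enrolment, since no accrual rate is given. The sample size of 90 per group is reproduced on its stated inputs and is not disputed here.

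**What to change.** Replace the Duration line with separate enrolment and follow-up periods, and add the following.

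- Every randomised participant is followed to T2 or withdrawal, and the study does not close at 6 months.
- The total duration is the enrolment period plus at least about 245 days after the last bonding. The one or two participants expected to be still unaligned then are followed on.
- The number of participants without T2 is reported by arm.

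The enrolment period should rest on the department's own accrual estimate. The design, the outcome and the planned test stay as they are. The cost is a few lines of text and a calendar longer than the 6 months now stated.

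### Does the 219.95-day steel mean attributed to reference 12, reported elsewhere as 176.15 days, undermine the sample size?

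*Combined protocol and SAP*

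**What the plan says.** Under Materials and Methods, the Sample Size paragraph takes its inputs by "assuming the mean duration of 224.95 ± 8.7 days for Elastomeric ligature group" and a "mean duration of 219.95 ± 9.82 days for steel ligature group". Citation 12 follows the steel figure. The paragraph concludes that 90 participants per group "will detect a 5 days difference in mean duration, with 95% power at 5% significance level".

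The background text before the Objective summarises two earlier studies. For reference 12 it gives: "elastomeric ligature was 224.95 ± 8.702 days while in steel ligature was 176.15 ± 9.81 days". For reference 11 it gives: "elastomeric ligature was 176.3 ± 11.08 days while in steel ligature was 175.56 ± 9.41 days". It then uses the disagreement between them to motivate the trial: "Owing to the contradictory results of the aforementioned studies this study would put to rest the contradictions".

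Nowhere does the protocol say whether 5 days is a published difference or one the investigators chose.

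**The concern.** One reference appears to carry two steel means, 176.15 and 219.95 days. Rounding cannot explain a gap of 43.8 days. The elastomeric mean agrees in both places, so the mismatch falls on the one figure that carries the citation directly. The steel SD is also printed as 9.81 in one place and 9.82 in the other.

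The planning difference drives the sample size. A reader who took 5 days as reference 12's finding would judge it differently from one who knew it was chosen. If the steel mean were a transcription error in a figure that the calculation depends on, the 90 per group could rest on a wrong input. If the error were instead in the background, the argument that earlier studies conflict would lose some force.

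**Working it through.** **Inputs.** Sample Size paragraph: elastomeric 224.95 ± 8.7, steel 219.95 ± 9.82, difference 5 days, power 95%, significance level 5%, 90 per group. Background: reference 12, elastomeric 224.95 ± 8.702 and steel 176.15 ± 9.81; reference 11, elastomeric 176.3 ± 11.08 and steel 175.56 ± 9.41. The protocol does not state sidedness. Two-sided is assumed because it reproduces the stated number; one-sided would give 75 per group.

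**1. Reproduce the plan's figure.** For two means with equal allocation,

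n per group = (SD₁² + SD₂²)(z₀.₉₇₅ + z₀.₉₅)² / d², where (1.960 + 1.645)² = 12.995 with unrounded z.

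- SD₁² + SD₂² = 8.7² + 9.82² = 75.69 + 96.43 = 172.12
- n = 172.12 × 12.995 / 5² = 89.47, so 90 per group, as stated.

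Power at 90 per group: the standard error is √(172.12/90) = 1.383, and 5/1.383 − 1.960 = 1.656, which gives 95.1%. A t-based calculation gives 94.9%.

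**2. Does the SD discrepancy matter?** With the background SDs, 8.702² + 9.81² = 171.96, and n = 171.96 × 12.995 / 25 = 89.38, so again 90. The two mixed pairings give 89.37 and 89.49, also 90.

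**3. Does the steel mean matter?** It enters only through the difference.

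- Sample Size paragraph: 224.95 − 219.95 = 5.00 days
- Reference 12 as given in the background: 224.95 − 176.15 = 48.80 days
- Reference 11: 176.3 − 175.56 = 0.74 days
- Between the two steel means: 219.95 − 176.15 = 43.80 days

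Two readings are possible.

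- *219.95 is a planning value.* The target is 5 days, the SDs come from reference 12, and n = 90.
- *219.95 is reference 12's published mean.* The published difference is 5 days, and n = 90.

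The number is the same on both.

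**4. Would either reported difference have served better?**

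| Difference | SDs | n per group for 95% power | Standardised difference |
|---|---|---|---|
| 48.8 days | 8.702, 9.81 | 0.94 by the normal formula; 3 by the t-based calculation | 5.26 |
| 5 days | 8.7, 9.82 | 90 | 0.54 |
| 0.74 days | 11.08, 9.41 | 5,015 | 0.07 |

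The standardised difference is d / √((SD₁² + SD₂²)/2). Neither reported difference gives a realistic trial size. Five days lies between them, and it is about a tenth of the difference the background reports for reference 12, so it is cautious against that source.

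**5. Does the figure reach the analysis?** No. The Statistical Analysis section compares observed days to alignment between the two groups. No published mean enters the test.

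**The case for a change.** The best case for a correction is that the word introducing the assumptions covers both means, and the elastomeric one does match the background's account of reference 12. That word therefore does not mark the steel mean as constructed. The citation sits on the one value that does not match, and no sentence calls 5 days a target or gives a reason for it. On any reading, either a figure or an attribution is wrong.

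This much stands: the citation is loosely placed or one figure is misprinted, and a sentence giving the origin of the 5 days would have helped.

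It does not carry further. A steel mean exactly 5.00 days below the elastomeric mean, in a statement about the difference the trial can detect, reads most naturally as a subtracted target. The citation closes a compound clause and can be taken as the source of the elastomeric mean and the SDs. Nothing in the documents favours 219.95 as the published value.

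Even if it were published, the background would still describe studies that disagree. Their elastomeric means differ by 224.95 − 176.3 = 48.65 days, and the steel means would differ by 219.95 − 175.56 = 44.39 days. The SD mismatch is copy-editing: an unrounded value between 9.815 and 9.819 would print as 9.82 when rounded and 9.81 when truncated.

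**Conclusion.** The observation is accurate but calls for no change. The protocol attaches reference 12 to a steel mean 43.8 days above the one it reports from that reference elsewhere, most likely because a 5-day target was subtracted from the elastomeric mean and the citation left at the end of the clause. The stated 90 per group is correct for a 5-day difference with 95% power. It holds under all four pairings of the printed SDs and whichever steel mean reference 12 published. Moving the citation or labelling 5 days as chosen would alter no sample size, power, procedure, analysis or conclusion.

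This rests on two assumptions: that the test is two-sided, which the reproduced number supports, and that 5 days is the difference the investigators meant to detect, which the paragraph says directly. The target reading of 219.95 is an inference, because reference 12 itself was not available, but the result does not depend on it.

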1. Littles irregularity index before treatment: _____ mm

2. Lower brackets bond up (T1), Dated: _____ / _____ / _____.

3. Alignment reached (T2), Dated: _____ / _____ / _____.

4. Time to reach alignment in mandible (T2-T1) : _____ days

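### If alignment is dated only at the six-week appointments the plan describes, 95% power for a 5-day difference is not supported and each arm's mean days is overstated

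*Combined protocol and SAP*

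**What the plan says.** The Objective is the mean time, in days, to complete alignment of the lower anterior teeth in each arm. The Operational Definitions make alignment a "Littles irregularity index score of zero". The Data Collection Procedure adds three facts:

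- How the index is obtained: "Littles irregularity index will be calculated on mandibular casts using Castroviejo caliper".
- When casts are made: "Mandibular dental casts will be taken on the day of appliance placement (T1) and then on the day when alignment is reached (T2").
- When patients attend after bonding: "Adjustment appointments will be conducted at six-week intervals".

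The outcome is "The alignment time from the day of appliance placement to the day when alignment is reached (T2-T1"), recorded in days. The proforma in Annexure I has one field for it, "Alignment reached (T2), Dated", and none for the previous visit.

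The Sample Size paragraph assumes 224.95 ± 8.7 days (elastomeric) and 219.95 ± 9.82 days (steel) and concludes that "a sample of 90 participants per group will detect a 5 days difference in mean duration, with 95% power at 5% significance level". The Statistical Analysis section plans an independent-samples t test, with this exception: "In case of skewed data Mann-Whitney U test will be applied instead of independent samples t test".

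**The concern.** A cast needs a visit, and the only follow-up visits described are 42 days apart. The target difference of 5 days is about one-eighth of that interval (5/42 = 0.12). If T2 can only be an appointment date, each recorded time is the true time plus a delay of up to 42 days. The sample size makes no allowance for this.

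Two things are at stake. First, a true 5-day difference could be missed, and the null result then read as coming from a trial with 95% power. That matters here because the background text says the study will settle contradictory earlier results. Second, the absolute mean in days, which is what the Objective asks for, would be too high in both arms.

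**Working it through.** **Inputs.** Means 224.95 and 219.95, SDs 8.7 and 9.82, n = 90 per group, 5-day target, 5% significance (Sample Size); 42-day visit interval (Data Collection Procedure). Assumed: normal true times, no dropout, two-sided test, T2 = first visit at or after true alignment, and follow-up of everyone to about day 252.

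**1. The plan's figure reproduces.** n = (8.7² + 9.82²)(1.96 + 1.645)²/5² = 172.12 × 12.99/25 = 89.5, so 90. The standard error of the difference is √(172.12/90) = 1.38 days, and power is Φ(5/1.38 − 1.96) = 95.1%. This holds if alignment is dated to the day.

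**2. Delay uniform over w days.** Each arm's variance rises by w²/12.

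| w (days) | Sum of variances | SE of difference | Power |
|---|---|---|---|
| 0 | 172.1 | 1.38 | 95.1% |
| 7 | 180.3 | 1.42 | 94.2% |
| 14 | 204.8 | 1.51 | 91.2% |
| 42 | 466.1 | 2.28 | 59.4% |

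At w = 42 both means are 42/2 = 21 days too high. Simulating the t test gives about 59%. With 90 per group, 95% power then requires a difference of 3.605 × 2.28 = 8.2 days.

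**3. Visits exactly every 42 days from T1.** The relevant visits are days 210 and 252.

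- Aligned by day 210: elastomeric Φ((210 − 224.95)/8.7) = 4.3%; steel Φ((210 − 219.95)/9.82) = 15.5%. Nearly everyone else is recorded at day 252; 0.1% or fewer are later.
- Recorded means: elastomeric 252 − 42 × 0.0429 + 42 × 0.0009 = 250.24; steel 252 − 42 × 0.1555 + 42 × 0.0005 = 245.49.
- Overstatement: 250.24 − 224.95 = 25.3 days; 245.49 − 219.95 = 25.5 days.
- Recorded difference 4.75 days; recorded SDs 8.61 and 15.26; SE √((8.61² + 15.26²)/90) = 1.85.

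The normal approximation gives Φ(4.75/1.85 − 1.96) = 73%. Simulating the t test itself gives about 75%. The simulated value is preferred because the recorded data are almost two-valued.

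**4. Sensitivity only: the 42-day grid shifted by 0 to 41 days relative to the means.** Simulated t-test power runs from about 18% to 88% and reaches 95% at no position. The recorded difference runs from 1.3 to 9.1 days. Overstatement is 15.3 to 26.7 days (elastomeric) and 16.5 to 25.5 days (steel).

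**5. Switching to Mann-Whitney.** The plan gives no threshold for skewed data; here it is read as Shapiro-Wilk p < 0.05 in either arm. Simulated power under that rule is 74% on the exact grid and 58% at random phase, much as for the t test. Under assumed visit-to-visit drift with an SD of 1 to 7 days it falls to about 26-56%.

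**6. Validity.** With no true difference, the simulated false-positive rate was about 4-6% for the t test and 4-5% for the switching rule.

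**The case against.** **The plan does not say that T2 is an appointment date.** It says the T2 cast is made on the day alignment is reached, and it describes the six-week visits as being for adjustment. Extra visits are not excluded, and with dating to within 14 days power would be 91%, a minor loss. This stands as a limit: the reading is an inference. But no other contact or dating method is described, so the 95% still lacks its basis until the plan supplies one.

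**The planning SDs may already contain visit rounding.** The documents do not say how the cited study dated alignment, so the 59-60% may count some variation twice. Rounding alone over 42 days has an SD of 42/√12 = 12.1 days, above both planning SDs. With no patient variation at all, power would be Φ(5/√(2 × 147/90) − 1.96) = 79%, still short of 95%.

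**The background text gives a steel mean of 176.15 days, from the same reference.** With that mean, power is near 100%. This limits the practical consequence, but the stated claim concerns a 5-day difference, and the overstatement of the means remains.

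**Stronger readings a reader might infer.**

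- That the comparison is biased or the test invalid. It is not: the false-positive rate holds, and on the exact grid both arms are overstated almost equally.
- That 90 per group is a miscalculation. It is not: the arithmetic is correct for times dated to the day.
- That power is as low as 18% under the written schedule. If visits run six-weekly from T1, only the unshifted grid applies. The 18-88% range shows dependence on assumptions and does not forecast this trial's power.

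**Conclusion.** The point holds conditionally. Confidence is high that the 95% figure is unsupported as the plan stands and that appointment-dated means would be too high. It is not high for any single replacement percentage.

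The best-supported sizes are t-test power of about 75% on an exact 42-day grid and 59-60% if alignment falls at random within the interval. The corresponding overstatement of each mean is about 25 and 21 days, and 15 to 27 days over all grid positions. Irregular visits combined with the Mann-Whitney switch may lower power further.

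All these figures use the Sample Size means and SDs and assume complete follow-up to about day 252. That conflicts with the stated study duration of 6 months after approval: under the planning means and SDs, fewer than 0.01% of either arm would have aligned by day 183.

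**What to change.** 1. **Power statement.** Withdraw the unqualified 95%. Restate power for the 5-day target, naming how T2 is dated, which test is used and how long participants are followed. Obtain it by simulating the planned test, including the switch rule, once two matters are reconciled: the steel planning mean (219.95 in Sample Size, 176.15 in the background text) and the 6-month duration. If alignment is dated between appointments, say how and recompute on that basis.
2. **Outcome label.** If T2 is an appointment date, report T2-T1 as time to the first appointment at which alignment was observed, an upper bound on alignment time.
3. **Proforma.** Add the date of the appointment immediately before T2, so that each arm's mean can be given with a lower and an upper bound. State that the lower bound assumes alignment would have been recorded had it been present at that visit. Keep the planned test. An interval-censored estimate of the means is an optional sensitivity analysis: it depends on the assumed distribution and does not restore the planned precision.
4. **Consistency.** The six-week schedule and the 5-day target must be reconciled. No schedule is proposed here.

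The cost is a less favourable power statement and one extra date per participant, with no extra cast, visit or patient. The optional model may need software other than the SPSS version named.

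### The outcome exists only for participants who reach an index of zero, so the planned test compares only those who aligned and can be biased if follow-up ends early or slow participants leave.

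*Combined protocol and SAP*

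**What the plan says.** Operational Definitions sets alignment as "Littles irregularity index score of zero". Inclusion criterion 4 requires 7-9 mm at entry.

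Data Collection Procedure: "Mandibular dental casts will be taken on the day of appliance placement (T1) and then on the day when alignment is reached (T2"). Adjustment visits are six weeks apart, the archwire sequence continues until alignment, and T2-T1 is said to be recorded for every participant.

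Annexure I holds the baseline index, the T1 date, a line "Alignment reached (T2), Dated", and T2-T1 in days. It has no last-visit date and no field for not aligned or left.

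Statistical Analysis: "Independent Samples t Test will be applied to compare time of alignment in days between two groups (steel and elastomeric) at T2", with Mann-Whitney if the data are skewed.

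Sample Size: "a sample of 90 participants per group will detect a 5 days difference in mean duration, with 95% power at 5% significance level". The only time limit anywhere is the study duration of 6 months after approval of the synopsis. The documents give no maximum follow-up, analysis set, missing-data rule, censoring rule or allowance for loss.

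**The concern.** Measurement depends on the event. Someone who keeps a residual irregularity, leaves, or is still in treatment when the study closes has a blank T2 and drops out of either test. The comparison is then of days among those who aligned, not among those randomised. The plan relies on randomisation to control bias, but randomisation does not protect a comparison restricted afterwards by the outcome itself.

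The target difference is only 5 days, so a shift of one or two days matters. If slow participants are the ones without a T2, the arm with more of them loses its longest times and its mean looks shorter than it is.

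**Working it through.** **Inputs.** From Sample Size: "assuming the mean duration of 224.95 ± 8.7 days for Elastomeric ligature group"; "mean duration of 219.95 ± 9.82 days for steel ligature group"; 90 per group. From the introduction, first cited study: elastomeric 176.3 (SD 11.08), steel 175.56 (SD 9.41). Normality and a common stopping day c are assumptions.

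**The plan's own figure.** n = (8.7² + 9.82²)(1.96 + 1.645)²/5² = 172.12 × 12.995/25 = 89.5, rounded up to 90 (two-sided). It reproduces. The 90 contains no allowance for loss.

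**Effect of a common stop at day c.** With a = (c − mean)/SD, the share with an outcome is Φ(a), and the mean among those who aligned is mean − SD × φ(a)/Φ(a).

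Worked at day 230:
- Elastomeric: a = 5.05/8.7 = 0.580, Φ = 0.719, mean 220.87.
- Steel: a = 10.05/9.82 = 1.023, Φ = 0.847, mean 217.21.
- Difference: 220.87 − 217.21 = 3.66 days, against a true 5.00.

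| Stop at day | Steel with outcome | Elastomeric with outcome | Difference among aligned (days) |
|---|---|---|---|
| 210 | 15.5% | 4.3% | 1.6 |
| 220 | 50.2% | 28.5% | 2.4 |
| 230 | 84.7% | 71.9% | 3.7 |
| 240 | 97.9% | 95.8% | 4.7 |
| 252 | 99.9% | 99.9% | 5.0 |

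Day 252 is six visit intervals (6 × 42).

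**First cited study's values, stop at day 183 (about 6 months).** Steel has 78.5% observed with mean 172.06; elastomeric has 72.7% with mean 171.24. Elastomeric minus steel moves from 176.3 − 175.56 = +0.74 to −0.83 (unrounded means), so the sign reverses.

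**Other ways of losing participants (planning values, rates assumed).**
- Equal loss unrelated to progress, 10-30%: the difference changes by +0.01 to +0.03 days.
- Slowest 10% of elastomeric and 5% of steel lost: 4.4 days.
- Slowest 20% of elastomeric and 5% of steel lost: 3.0 days.
- Slowest 10% lost in both arms: 5.2 days, slightly wider because the steel SD is larger.

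**What a restricted mean would give at day 230.** Counting those not yet aligned as 230 days:
- Elastomeric: 0.7192 × 220.87 + 0.2808 × 230 = 223.43.
- Steel: 0.84695 × 217.21 + 0.15305 × 230 = 219.17.
- Difference: 4.3 days. This uses everyone randomised, but it is a difference up to day 230 and not the full 5.0.

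**The case against.** The strongest reply is that the plan sets no cut-off. Treatment runs until alignment and T2-T1 is to be recorded for everyone. Under the planning values, follow-up to about day 252 leaves almost nobody without an outcome and almost no bias. That is right about size, and it stands. But the plan does not commit to that follow-up, and it has no rule for those who leave.

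A reader might infer that omission always flatters the slower arm. The documents do not support that: they give no rate or pattern of loss by arm, and the scenarios above include negligible change and slight widening.

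A reader might also suppose that omitted participants would have aligned one or two visits later than average, so that a handful could erase the 5-day target. Such delays are 42/8.7 = 4.8 and 84/8.7 = 9.7 planning SDs, so they conflict with the plan's own spread and are not used here.

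Nor can one say that the information would be lost for good. A blank T2 still identifies non-aligners by arm, and the documents do not say that appointment dates go unrecorded elsewhere. The narrower point stands: the proforma does not collect them and the analysis does not use them.

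**Conclusion.** The concern holds in a conditional form. As written, the analysis can use only those who aligned. Bias is expected if follow-up ends before everyone aligns or if slow participants leave more often. Under a common stop and the planning values it takes 2.6 of the 5 days at day 220 (5.0 − 2.4), 1.3 at day 230, 0.3 at day 240 and almost none at day 252. These figures rest on normal times and on stopping days that the documents do not fix.

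The 6-month duration (about 183 days) is shorter than both planning means of about 220 and 225 days. If it bounded each participant's follow-up, almost nobody would have an outcome under the planning values (0.008% of steel). A reader might conclude that this will happen, but the documents do not say whether the 6 months covers follow-up. The two passages must be reconciled. The sample-size figure is correct for its inputs. This should be fixed before enrolment.

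**What to change.** 1. Add to Annexure I, for every randomised participant, the date of the last visit and the status on that date: aligned, not aligned or left.
2. State one common end of follow-up for the analysis, and reconcile the 6-month duration with the planning means.
3. Analyse all randomised participants from T1, with those not aligned censored at their last visit. Give Kaplan-Meier curves and, as the main result, the between-arm difference in restricted mean days to the common time.
4. Report the numbers not aligned and left, by arm.
5. As a sensitivity analysis, rank those without alignment last in the Mann-Whitney test, because leaving may be related to slow progress.
6. Keep the t test among aligned participants as a secondary description.

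**Cost.** Two proforma fields, one paragraph in Statistical Analysis and a little more analysis work. No extra cast is needed, because whether alignment has been reached must already be judged in order to trigger the T2 cast. The restricted mean depends on the chosen time (4.3 days at day 230 above), so that time should be fixed in advance. Censoring assumes that leaving is unrelated to progress, which is why item 5 is needed.
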